The ITT analysis was suitable for this crossover design ³ as the placebo condition was treated identically to the active drug condition (route, administration and laboratory procedures). Distributional characteristics of outcome measures were examined to evaluate similarity to the normal distribution. detailed descriptive analysis of demographics, substance use, and clinical characteristics. The cortisol had a kurtosis in excess of four; consequently, an outlier analysis was performed and a total of 5 outliers falling outside of ±3 interguartile range were Winsorized as recommended ⁴. Comparisons with these characteristics, in relation to enrolled versus completer status, were performed using *t*-tests to analyze continuous variables (age) and χ^2 for categorical variables (sex, race, medication status). Attrition rates between the screening visit and follow-up visit were examined descriptively to assess for potential bias. In addition, a logistic regression was performed to test for possible bias due to period (placebo first, then oxytocin and oxytocin first, then placebo) or medication carryover (placebo and oxytocin), as done in our prior cross-over trial ⁵. This study tested the feasibility of the combined study design, the safety and tolerability of IN oxytocin and yohimbine, and the potential value of testing IN oxytocin as adjunct therapy in an appropriately-powered larger RCT. In selecting a target sample size, we balanced power considerations and feasibility given the preliminary nature of this trial. Because of the within-subjects design, power to test the effects of the study drug was optimized for this modest sample size. For the safety and tolerability outcomes (primary) adverse events, difference was detected based on a

judgement concerning the minimal effect, which has clinical relevance in the management of patients. In a noninferiority trial, the exact sample size could not be fixed in advance because it depends upon the chosen stopping guidelines ⁶.

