Outcomes: Primary (craving) and secondary (safety and tolerability) outcomes were assessed in realtime in the laboratory. Seven-day oxytocin administration was compared to the oxytocin-matched placebo condition during the CR procedure, in which noradrenergic activation produced by yohimbine or yohimbinematched placebo condition (2X2 design) was measured. We used Generalized Linear Model (GLM) with modelbased estimator in the covariance matrix, with medication (oxytocin/placebo) and noradrenergic activation (yohimbine/placebo) as within-subject factors. The model was specified to evaluate the effect of drug (oxytocin/placebo) by noradrenergic (vohimbine/placebo) interaction, main effect of the drug, and main effect of noradrenergic activation. Craving was assessed using the DDQ with time coded as: t_0 =relaxation, t_1 =interaction with drug paraphernalia/opioid auditory cues and t_2 =opioid use video. Safety and tolerability were assessed using: SBP, DBP, HR (vital signs), HAM-A and STAI (anxiety). The STAI y1 (state) was included as an additional safety measure for anxiety to ensure participants were not experiencing acute symptoms of anxiety within the laboratory. The STAI y2 (trait) was inserted as a covariate in the model to control for baseline anxiety level, along with stress (PSS), HPA (cortisol), and noradrenergic response (α -amylase). Time at laboratory sessions was coded as: t_0 =baseline, t_{45min} =45-min after yohimbine administration, and t_{90min} =post cue-exposure to specifically evaluate the contribution of each laboratory procedure (vohimbine and CR). Withdrawal symptoms (COWS) and AEs were assessed at specific timepoints: t_0 =pre-laboratory and t_1 =post-laboratory procedures.

Other outcomes (safety and tolerability) were measured retrospectively during the one-week outpatient setting and included the: COWS (withdrawal), anxiety (HAM-A and STAI), stress (PSS), depression (HAM-D) and AEs. The other outcomes were analyzed using ANOVA test and the number of AEs via a χ^2 test. For missing data approach, we first categorized missing data as missing completely at random (MCAR), missing at random (MAR) or missing not at random (MNAR)⁷. Analysis with GLM (using all available pairs of data to model missing values with maximum likelihood estimation) was deemed suitable for our analyses because no systematic differences existed between participants with missing data and those with complete data (MCAR)⁸.

Missing data reporting ⁹

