- 1. Amount of missing data in the dataset:
 - a. Oxytocin condition: 10% did not receive either oxytocin or placebo condition (within subject, *n*=16; between subject, *n*=4)
 - b. Yohimbine condition: 11.12% did not receive yohimbine condition (yohimbine, *n*=14; placebo, *n*=16; no yohimbine, *n*=4):

- 2. Reason for missing:
 - a. Oxytocin condition: change from between subject to within subject design
 - b. Yohimbine condition: safety concerns due to past history of cardiovascular disease and/or current hypertension (*n*=3), stroke (*n*=1)

3. Consequences:

- a. *Oxytocin condition*: no differences between participants with and without missing values except there were no subject taking methadone in the subjects with missing values.
- b. *Yohimbine condition*: no differences between participants with and without missing values except there were cardiovascular concerns in the subjects with missing values.
- 4. *Method*: GLM with MNAR using all available pairs of data to model missing values with maximum likelihood estimation
- 5. Software: IBM SPSS Statistics for Windows, version 29 (IBM Corp., Armonk, NY, USA)

All statistical analyses were performed after participants had completed their follow-up visits and the study database had been locked. The results were presented using summary statistics: number of subjects (n); mean (M); standard deviation (SD) or frequency distributions (%) and effect size was reported as Cohen's d.

All statistical procedures were performed by IBM SPSS Statistics for Windows, version 29 (IBM Corp., Armonk, NY, USA), and GraphPad Prism (v.10) was used to generate figures (La Jolla, CA, USA). All statistical tests were two-tailed, and statistical significance was accepted if an alpha value p<.05 was obtained.

References

1. FDA. Changes or modifications during the conduct of a clinical investigation; final guidance for industry and CDRH staff. 20012001.

Schulz K, Altman D, Moher D. Consolidated Standards of Reporting Trials Group CONSORT
2010 Statement: Updated Guidelines for Reporting Parallel Group Randomised Trials. Bmj.
2010;340:c332.

4. Tukey JW. The future of data analysis. The annals of mathematical statistics. 1962;33(1):1-67.

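### The SAP explains the missing safety sample size by non-inferiority and stopping guidelines that it never defines, and analyses safety only by two-sided difference tests without confidence intervals

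*SAP*

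**What the plan says.** The sample-size remarks are in the SAP, Statistical analysis. For the trial as a whole the SAP says "In selecting a target sample size, we balanced power considerations and feasibility given the preliminary nature of this trial", and gives no number. It then turns to safety, which it labels primary: "For the safety and tolerability outcomes (primary) adverse events, difference was detected based on a". After a break in the extracted text, the same sentence resumes with "judgement concerning the minimal effect, which has clinical relevance in the management of patients". No value, scale or direction is attached to that minimal effect. The next sentence is "In a noninferiority trial, the exact sample size could not be fixed in advance because it depends upon the chosen stopping guidelines", with a citation to a general guideline on statistical principles.

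The Outcomes paragraph of the SAP describes the analysis. It opens with "Primary (craving) and secondary (safety and tolerability) outcomes were assessed in realtime in the laboratory", which reverses the label given to safety just before. It describes a GLM with oxytocin and yohimbine as within-subject factors, and lists blood pressure, heart rate, HAM-A and STAI as the in-laboratory safety measures. Outcomes collected retrospectively over the outpatient week are tested by ANOVA, and "the number of AEs via a χ^2 test".

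The end of the Missing data reporting section adds "All statistical tests were two-tailed, and statistical significance was accepted if an alpha value p<.05 was obtained" and "All statistical analyses were performed after participants had completed their follow-up visits and the study database had been locked". The summaries listed there are n, mean, SD, frequencies and Cohen's d. Confidence intervals are not among them.

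In the Protocol, Aim 3 (Specific Aims and Study Objectives) is to assess safety and tolerability, with no hypothesis. The one sample-size calculation (Participant Population) concerns craving.

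**The concern.** A non-inferiority claim needs a margin fixed in advance and a confidence limit, or equivalent one-sided test, set against it. A sample size that depends on stopping guidelines needs those guidelines and at least one interim look. The supplied text has none of these, and it places all statistical analyses after database lock. The SAP therefore explains the absence of a safety sample size by a design feature that the described trial does not show.

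The tests that are planned answer a different question. A two-sided test that fails to reject says only that a difference was not shown. In a small trial it will usually fail to reject even if AEs are materially more frequent on oxytocin. When non-inferiority language stands next to such tests, and no interval shows what has been ruled out, a non-significant p-value could be taken as support for safety. The smaller the trial, the more easily that happens.

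Two further weaknesses add to this. As named, the χ² test takes no account of the same participants contributing to both conditions, nor of one participant having several AEs. And safety is primary in one paragraph and secondary in the next, so the weight its result should carry is unsettled.

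**Working it through.** **1. The plan's own figure.** Protocol, Participant Population: f = 0.35, α = 0.05, two groups, three covariates, N = 67 for power 0.80. With a noncentral F distribution, numerator df = 1, denominator df = 67 − 2 − 3 = 62 and λ = 0.35² × 67 = 8.21, power is 0.805. The figure reproduces. It is a superiority calculation for craving and gives no size, power or margin for safety.

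**2. Non-inferiority elements in the supplied text.**

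| Element | Found? |
|---|---|
| Numeric margin | No; an unquantified judgement about a minimal effect |
| Non-inferiority hypothesis | No; Aim 3 is only to assess |
| One-sided bound or CI criterion | No; all tests two-tailed at .05 |
| Stopping guideline or interim look | No; all analyses after database lock |

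**3. Number of participants.** SAP, Missing data reporting: 16 within-subject and 4 between-subject, 20 in all. The stated 10% missing agrees with this: 4 missing conditions out of 20 × 2 = 40.

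**4. Precision of the paired AE risk difference.** The documents give no AE rates, so the proportion ψ of participants with an AE under one condition only is an assumption. With no net difference, the 95% half-width is 1.96 × √(ψ/16):

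| ψ (assumed) | Half-width |
|---|---|
| 0.10 | 1.96 × √(0.10/16) = 0.155 |
| 0.20 | 0.219 |
| 0.30 | 0.268 |
| 0.40 | 0.310 |

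That is about 16 to 31 percentage points. These are large-sample values resting on roughly 2 to 6 discordant pairs (0.10 × 16 = 1.6; 0.40 × 16 = 6.4), so they indicate size only.

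**5. Zero events.** If no participant had a given event, the one-sided 95% upper limit is 1 − 0.05^(1/n). For n = 16 it is 0.171; for n = 20 it is 0.139. The number exposed to oxytocin lies between 16 and 20, because the SAP does not say which condition the 4 between-subject participants received.

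**6. Power of the difference test.** Treating conditions as independent with n = 16 to 20 each, power = Φ{[|p₁ − p₂| − 1.96√(2p̄(1 − p̄)/n)] / √([p₁(1 − p₁) + p₂(1 − p₂)]/n)}. The AE rates are assumed:

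| AE rates | Power, n = 16 | Power, n = 20 |
|---|---|---|
| 20% v 30% | 0.09 | 0.11 |
| 20% v 40% | 0.23 | 0.28 |
| 10% v 30% | 0.29 | 0.35 |

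**7. What a paired non-inferiority comparison would need.** With one-sided α = 0.025, power 0.80 and no true difference, n = ψ(1.960 + 0.842)²/margin². For ψ = 0.10 to 0.40 this gives 79–314 participants for a 10-point margin, 20–79 for 20 points and 9–35 for 30 points. These margins are illustrations, since the SAP states none.

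**The case against.** The strongest reply is that one stray sentence is being given too much weight. The sentence is a general remark with a citation. It does not say that this trial is a non-inferiority trial, and the basis the SAP gives for its target size is a balance of power and feasibility in a preliminary study meant to inform a larger one. Safety is also not reported by p-values alone, since means, SDs, frequencies and Cohen's d are planned. The precision figures rest on an assumed discordance, a large-sample formula and AE status per participant, whereas the SAP tests the number of AEs.

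Much of this stands, and it rules out several stronger readings that a reader might infer:

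- **That the plan will treat p > .05 as proof of safety.** No sentence says so. The text leaves room for that misreading; it does not prescribe it.
- **That Aim 3 sets out to establish safety.** The Protocol's verb is assess, which carries no confirmatory claim.
- **That the trial has no stopping rule.** The Data and Safety Monitoring Plan is Attachment D and was not available. The statement is limited to the supplied Protocol and SAP text. A safety halting rule in Attachment D would still not supply a margin or a non-inferiority analysis.
- **That no minimal effect was considered.** One is mentioned; what is lacking is its value.
- **That all safety data go through χ² and ANOVA.** The in-laboratory measures appear to fall under the within-subject GLM, although that is also a test for a difference.

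What the reply does not remove is that the sentence follows directly on the safety outcomes and is the only reason offered there for having no exact safety sample size. Calling the trial preliminary argues for estimates with intervals.

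**Conclusion.** The concern holds in this limited form. The SAP invokes non-inferiority and stopping guidelines for the safety outcomes, while the supplied documents define neither, plan only two-sided difference tests and list no confidence intervals.

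With 16 within-subject participants, the half-width of about 16–31 points (assumed discordance 10–40%, no net difference) means that a non-significant result would be compatible with a considerable excess of AEs on oxytocin. The zero-event limits of 17% and 14% are hypothetical, because the documents report no AE counts. Neither set of figures shows that oxytocin is unsafe; they show how little a non-significant test could exclude.

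This should be corrected, because safety is a stated aim and its rank among the outcomes is contradictory. It does not affect the craving analysis.

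**What to change.** 1. Delete the sentence on non-inferiority and stopping guidelines. A margin added now, with the database locked, would not be prespecified, so deletion is cleaner than completing the framework.
2. Replace the χ² test on AEs with the oxytocin-minus-placebo risk difference in the within-subject participants, with a 95% CI from a small-sample method for paired proportions. Count participants with at least one AE, and list the number of events alongside. Describe the 4 between-subject participants separately.
3. Report mean paired differences in vital signs and anxiety, each with a 95% CI.
4. Word the safety conclusion by the upper confidence limit, that is, by the largest excess the data do not rule out, and not by p > .05.
5. Reconcile the two paragraphs of the SAP so that safety is either primary or secondary throughout.

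The cost is a revision of SAP wording and some intervals from data already collected. The safety statement will be less favourable than a bare report of no significant difference.

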Oxytocin, Stress, Craving, Opioid Use Disorder (OSCO)

STATISTICAL ANALYSIS PLAN

[name], PhD [name] [contact]; [contact] [contact]

ORIGINAL: 2019 AUGUST 08 REVISED: 2022 MAY 05

Clinical trial registration: Clinicaltrials.gov; NCT04051619

IND/FDA: 135570, oxytocin and yohimbine (Holder: [name])

Table of Contents

Study design, setting and approval	3
Statistical analysis	3
Missing data reporting	4
References	6

Study design, setting and approval

This was a Phase 1, outpatient, randomized, double-blind, cross-over (2x2 design with oxytocin and yohimbine), placebo-controlled, human laboratory study (**Figure 1**). The trial took place at the Center for Alcohol and Addiction Studies, Brown University, Providence, RI, USA from 2019-2023. The clinical protocol was approved by the Brown University Institutional Review Board (IRB), received an FDA Investigational New Drug (IND135570), and was registered on clinicaltrials.gov (NCT04051619). The study was initiated as a between-subjects design. However, following the COVID-19 pandemic, in order to speed up recruitment, the study was changed to a within-subjects crossover design. This modification in the clinical protocol was executed following the FDA Guidance Document on Changes or Modification during conduct of Clinical Investigations ¹. After receiving approval from the Brown University IRB in November 2021, the FDA was notified in an annual progress report and the study design was updated on clinicaltrials.gov in February 2022.

Statistical analysis

For all outcomes, we utilized an intention-to-treat (ITT) approach, where participants were examined based on their *a priori* randomized protocol and received at least one dose of the study medication (oxytocin or oxytocin-matched placebo)²

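### The craving GLM relies on a model-based covariance but names no correlation structure and no period term, so the level of the oxytocin test cannot be judged and a period shift would go unadjusted

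*SAP*

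**What the plan says.** The SAP's Outcomes paragraph describes the craving analysis: "We used Generalized Linear Model (GLM) with modelbased estimator in the covariance matrix", with medication and yohimbine as within-subject factors. On the effects it says: "The model was specified to evaluate the effect of drug (oxytocin/placebo) by noradrenergic (vohimbine/placebo) interaction, main effect of the drug", followed by the yohimbine main effect. On covariates: "The STAI y2 (trait) was inserted as a covariate in the model to control for baseline anxiety level", together with PSS, cortisol and alpha-amylase; whether these enter the craving model or only the safety models is not clear. On repeated scores: "Craving was assessed using the DDQ with time coded as" three points within a session. With four sessions in the Protocol (Part III, section 3), that is up to 12 scores per person. No correlation structure, random effect or period term is named.

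Period appears only under Statistical analysis, where "a logistic regression was performed to test for possible bias due to period (placebo first, then oxytocin and oxytocin first, then placebo") or carryover. The levels given for period are the two sequences. The outcome of that regression is not named, and nothing says how its result would change the craving model.

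The design changed part-way: "in order to speed up recruitment, the study was changed to a within-subjects crossover design". Missing data reporting gives "10% did not receive either oxytocin or placebo condition (within subject" n=16, between subject n=4). The Protocol plans counterbalanced order and also lets earlier completers return for the opposite condition. Tests are two-tailed, and "statistical significance was accepted if an alpha value p<.05 was obtained".

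**The concern.** Oxytocin changes only between weeks, so its effect must be judged against week-to-week variation within a person. Scores from one session, or one week, are likely to be more alike than scores from different weeks. A structure that ignores this treats the scores within a week as more independent information than they are, and a model-based standard error does not correct for it. The SAP does not say which structure was used, so a reader cannot tell whether a nominal 5% is near 5%.

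Separately, if craving drifts from the first treatment week to the second and the two sequences differ in size, part of that drift is counted as an oxytocin effect. The trial is meant to inform whether a larger trial is worthwhile, so a false positive or a shifted estimate would feed into that decision.

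**Working it through.** **Plan's own figures.** The 10% reproduces: 4 missing condition cells out of 20 × 2 = 40. The SAP gives no error rate for the craving model beyond the nominal 5%. The Protocol's N = 67 reproduces (power 0.805), but for a between-group ANCOVA, so it says nothing about the crossover model.

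**Inputs.** From the SAP: 16 people with both conditions, 4 with one. From the Protocol and SAP: 2 sessions per week, 3 DDQ scores per session. Assumed, because the documents give none: participant SD 1, residual SD 0.6, five pairs of week/session SD, sequences 8/8, one-condition people 2/2, no oxytocin effect.

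**Simulated type I error (%) at nominal 5%.**

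| Analysis | 0/0 | 0.1/0.1 | 0.2/0.2 | 0.3/0.3 | 0.6/0.5 |
|---|---|---|---|---|---|
| Oxytocin, all 12 scores, exchangeable | 6 | 7 | 14 | 21 | 35 |
| Same, plus period term | 6 | 7 | 14 | 21 | 35 |
| Oxytocin, all 12 scores, independence | 3 | 3 | 6 | 9 | 17 |
| Oxytocin, one value per session, exchangeable | 6 | 6 | 6 | 9 | 12 |
| Oxytocin, session means, exchangeable | 5 | 6 | 9 | 12 | 16 |
| Interaction, all 12 scores, exchangeable | 4 | 5 | 6 | 9 | 12 |
| Interaction, one value per session, exchangeable | 5 | 6 | 6 | 4 | 3 |
| Mixed model: participant, week, session, period, sequence; Kenward-Roger | 3 | 5 | 6 | 6 | 4 |

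A repeat run gave 5–35% (12 scores), 5–11% (one value), 8–16% (session means) and 2–11% (interaction). The differences of a few points are of the order of simulation error. The period-adjusted per-person difference test in the 16 gave 5–6%.

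**Hand check at week/session SD 0.6/0.5.** For one crossover person the true variance of the oxytocin-minus-placebo difference in week means is 2(σw² + σs²/2 + σe²/6) = 2(0.36 + 0.125 + 0.06) = 1.09.

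- *All 12 scores.* Total variance is 1 + 0.36 + 0.25 + 0.36 = 1.97. Each score has 2 partners in its session (covariance 1.61), 3 in the other session of the week (1.36) and 6 in the other week (1.00). The mean is (3.22 + 4.08 + 6.00)/11 = 1.209. Exchangeable therefore takes 1.97 − 1.209 = 0.761 as within-person variance and 2 × 0.761/6 = 0.254 as the variance of the difference. The standard error is √(0.254/1.09) = 0.48 of its true value, and 2[1 − Φ(1.96 × 0.48)] is about 35%.
- *One value per session.* True variance is 2(0.36 + (0.25 + 0.36)/2) = 1.33. Mean covariance is (1.36 + 2 × 1.00)/3 = 1.12, so exchangeable takes 1.97 − 1.12 = 0.85. The ratio is √(0.85/1.33) = 0.80, giving about 12%.

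**Period.** With shift δ and sequence sizes n₁ and n₂, the unadjusted bias in the 16 is δ(n₁ − n₂)/16. With an assumed δ of 0.5 participant SD:

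- 8/8: 0.00
- 9/7: 0.5 × 2/16 = 0.06
- 10/6: 0.5 × 4/16 = 0.125 (simulated 0.11–0.13)

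With period in the model the bias is 0.00. At 10/6 with week/session SD 0, exchangeable rejects 24.6% of the time and the period-adjusted per-person test 4.9%.

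**Returning completers.** Suppose 4 of the 16 returned, 3 in one sequence and 1 in the other, and only they carry the 0.5 shift. A common period term then still leaves 0.5 × (3/8 − 1/8)/2 = 0.06. Leaving them out gives 0.00.

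**The case against.** The strongest objection is about size. The 35% needs all 12 scores in one exchangeable model and large week and session variation. The SAP names only two within-subject factors, which make four cells, and does not say that the three DDQ times enter jointly. With one value per session the excess is small except at the largest variances. This stands, and the range has to be read by layout.

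Second, the SAP lists the interaction first, and the Protocol's Aim 1 concerns craving after yohimbine. A shift common to a whole oxytocin week cancels from the interaction in people with complete sessions, so that test is much less exposed. This also stands.

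Third, order is counterbalanced by plan, and nothing in the documents shows an imbalance. Under simple 1:1 allocation a split of 10/6 or worse has probability 2 × P(Bin(16, 0.5) ≤ 6) = 45%, but effective counterbalancing would lower that. Bias is therefore possible, not shown. It cannot be ruled out either: the design changed part-way, completers could return, and the realised split is not reported.

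Fourth, the SAP does test period and carryover. That test may flag a problem, but as described it does not adjust the craving estimate.

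Fifth, the SAP calls craving primary under Outcomes but attaches the word to safety and tolerability under Statistical analysis, and it describes a preliminary Phase 1 study. That limits the weight a 5% threshold on craving should carry.

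**Conclusion.** The gap is real: a model-based covariance with no stated structure, and no period term in the craving model. Under the assumed variances the oxytocin main-effect test under exchangeable runs at about 5–35% with 12 scores per person, about 5–11% with one value per session and up to about 16% with session means. Independence can be conservative (3%) or liberal (17%). The interaction runs at about 2–11% under exchangeable. Period bias is 0.00, 0.06 and about 0.12 at 8/8, 9/7 and 10/6, for an assumed 0.5 SD shift.

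Three stronger readings are tempting and not supported. A reader might infer that the reported oxytocin test had an error rate near 35%; the structure, the DDQ rows used and the variances are all unknown. A reader might infer that the estimate is biased by period; neither the split nor any shift is given. A reader might infer that a period term alone repairs the test; it removes the bias from a common shift but leaves the exchangeable error rate where it was. What the documents support is that the level cannot be judged and the adjustment is absent. In a preliminary study this should be put right, but it does not invalidate the trial.

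**What to change.** 1. Add period to the craving model, entering the 4 one-condition participants in the period in which they were treated. Do not rely on the logistic regression as the period adjustment.
2. State which DDQ rows enter. Use a covariance that allows extra correlation within oxytocin week and within session, with small-sample inference such as Kenward-Roger. With one row per session, the week level is what remains to be added to the participant effect.
3. Report the period-adjusted per-person oxytocin-minus-placebo difference with a 95% CI in the 16 crossover participants, and repeat it without any re-enrolled completers. This needs no covariance model.
4. Report the realised sequence split and the number re-enrolled.

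The database is locked and the analyses are done, so the new results should be labelled as sensitivity analyses. The cost is SAP wording, a rerun on existing data and one degree of freedom for period. The interval may widen. In the five settings with all 12 scores, the mixed-model 95% CI was 1.1 to 2.2 times as wide as under exchangeable (0.190/0.174 to 0.540/0.244) and 0.6 to 1.5 times as wide as under independence (0.190/0.304 to 0.540/0.367).
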